6.1.2 Pazopanib

The most common adverse events (AEs) reported to date include diarrhea, fatigue, nausea, hypertension, hair color changes (hair depigmentation), anorexia, vomiting, dysgeusia,

headache, abdominal pain, rash, aspartate aminotransferase (AST) and alanine aminotransferase (ALT) increases, constipation, cough, and arthralgia. Most of these events were Grade 1 or 2 using the NCI Common Terminology Criteria for Adverse Events Version 4.0 (NCI-CTCAE). The most frequent Grade 3 or 4 events were hypertension, fatigue, diarrhea, and AST and ALT increases. Less common AEs of note include hand-foot syndrome, mucositis/stomatitis, proteinuria, venous thrombotic events, and bleeding. Intestinal perforations and arterial thromboses were uncommon.

The most common serious adverse events (SAEs) occurring in subjects enrolled in pazopanib studies regardless of treatment assignment include vomiting, diarrhea, abdominal pain, hypertension/hypertensive crisis, dyspnea, pleural effusion, pyrexia, anemia, dehydration, and pulmonary embolism.

Evaluation of the safety and efficacy of pazopanib in advanced RCC subjects include a recently completed Phase II study in subjects with advanced RCC, and a Phase III randomized, double-blind study against placebo which completed enrolment in April, 2007 and is currently on-going. To date, 660 subjects with advanced/metastatic RCC have been enrolled in these two clinical trials. Safety data from the Phase II RCC trial VEG102616 (n=225) are summarized here. The most common AEs (defined as AEs experienced by \geq 10% of subjects) regardless of causality in decreasing order of frequency were diarrhea (63%), fatigue (46%), hair color change (43%), nausea (42%), hypertension (41%), anorexia (24%), dysgeusia (24%), vomiting (20%), headache (20%), cough (17%), abdominal pain (16%), rash (16%), constipation (15%), ALT elevation (14%), arthralgia (13%), AST elevation (12%), back pain (12%), dizziness (12%), handfoot syndrome (11%), alopecia, (10%), dyspepsia (10%), and peripheral edema (10%). The majority of these events were Grade 1 and 2 with hypertension being observed in 9% of subjects as a Grade 3 event.

The most common hematological toxicities of any grade (graded according to NCI-CTCAE) include lymphopenia (47%), thrombocytopenia (28%), neutropenia (23%), and anemia (26%) with combined Grade 3 and 4 abnormalities occurring in 7%, 3%, <1%, and 4% of subjects, respectively. The most common chemistry abnormality was hyperglycemia, observed in 46% of subjects (of which 2% were Grade 3 and no Grade 4). Hyponatremia of any grade was observed in 37% of subjects, with Grade 3 or Grade 4 hyponatremia in 8% of subjects. Hyperkalemia of any grade was reported in 27% of subjects, with Grade 3 or 4 hyperkalemia in 5% of subjects. Hyponatremia and hyperkalemia have not occurred concurrently in the same subject to indicate adrenal insufficiency. Elevations in amylase and lipase of any grade were reported in 23% and 27% of subjects, respectively, with Grade 3 or Grade 4 events in 4% and 9% of subjects, respectively. There were 2 reports of pancreatitis. Increase in TSH was reported in 28% of subjects and a decrease in thyroxine (T4) in 1% of subjects. Three subjects initiated treatment with thyroid replacement therapy (synthroid or levothyroxine) during the study.

ALT elevations of any Grade were reported in 53% of subjects with Grade 3 and Grade 4 elevations in 9% and <1% of subjects, respectively. AST elevations were reported in 53% of subjects with Grade 3 and Grade 4 elevations in 5% and <1% of subjects, respectively.

Hyperbilirubinemia of any Grade occurred in 28% of subjects with Grade 3 elevations in <1% of subjects. No Grade 4 elevations have been reported. Concomitant elevations in transaminases and bilirubin have been observed in 2 (<1%) subjects. Neither of these patients met the criteria for Hy's rule. Risk factors that may have contributed to the liver dysfunction were identified in the some of these subjects, (e.g., large mass at the porta hepatis, hepatotoxic concomitant medications). Liver enzyme elevations were reversible upon dose interruption. Two patterns of transaminase changes have been observed:

- (1) transaminase elevations that declined over time without dose interruption.
- (2) transaminase elevations that declined over time upon dose interruption. In some subjects, elevations in transaminase recurred upon rechallenging and these subjects were permanently discontinued from study treatment.

Serial adrenocorticotrophic hormone (ACTH) stimulation tests were conducted in two Phase I and two Phase II trials in cancer subjects with data available in 47 subjects. Twenty-one of them had data beyond 24 weeks and 5 subjects had data beyond 52 weeks. None of these 47 subjects had adrenal insufficiency.

Certain uncommon AEs with significant clinical consequences reported in pazopanib clinical trials (denominator for total subject enrolment n=1000 used for calculating frequency) include pulmonary embolism (0.6%), venous thrombosis (0.3%), venous thrombosis and pulmonary embolism (0.2%), serious hemorrhage (1.4%), bowel perforation (0.5%), myocardial infarction/angina (0.7%), cerebrovascular accidents/transient ischemia (0.6%), cardiac failure (0.2%), atrial fibrillation (0.3%), renal failure (0.8%) and seizures (0.3%)

6.2 Toxicity Management

All toxicities, both during and after the DLT-determining period will follow the guidelines laid out here in sections 6.2 and 6.3.

For definition of a DLT, refer back to section 5.4.

6.2.1 Management of stomatitis/oral mucositis/mouth ulcers

Adverse Drug Reaction	Severity	Everolimus Dose Adjustment and Management Recommendations
Stomatitis	Grade 1	No dose adjustment required. Manage with non-alcoholic or salt water (0.9%) mouth wash severaltimes a day.
	Grade 2	Temporary dose interruption until recovery to grade ≤ 1 . Re-initiate everolimus at same dose. If stomatitis recurs at grade 2, interrupt dose until recovery to grade ≤ 1 . Re-initiate everolimus at lower dose. Manage with topical analgesic mouth treatments (e.g. benzocaine, butyl aminobenzoate, tetracaine hydrochloride, methol or phenol) with or without topical corticosteroids (i.e. triamcinolone oral paste)*.
	Grade 3	Temporary dose interruption until recovery to grade ≤ 1 . Re-initiate everolimus at lower dose. Manage with topical analgesic mouth treatments (i.e. benzocaine, butyl aminobenzoate, tetracaine hydrochloride, methol or phenol) with or without topical corticosteroids (i.e. triamcinolone oral paste)*
	Grade 4	Discontinue everolimus and treat with appropriate medical therapy.

* using agents containing hydrogen peroxide, iodine, and thyme derivatives in management of stomatitis as they may worsen mouth ulcers.

Stomatitis/oral mucositis/mouth ulcers due to everolimus should be treated using local supportive care. Investigators in earlier trials have described the oral toxicities associated with everolimus as mouth ulcers, rather than mucositis or stomatitis. If the examination reveals mouth ulcers rather than a more general inflammation of the mouth, the adverse event should be classified as mouth ulcers. Please follow the paradigm below for treatment of stomatitis/oral mucositis/mouth ulcers:

1. For mild toxicity (Grade 1), use conservative measures such as **non-alcoholic mouth wash or salt water (0.9%) mouth wash** several times a day until resolution.
2. For more severe toxicity (Grade 2 in which case patients have pain but are able to maintain adequate oral alimentation, or Grade 3 in which case patients cannot maintain adequate oral alimentation), the suggested treatments are **topical analgesic mouth treatments (i.e., local anesthetics such as benzocaine, butyl aminobenzoate, tetracaine hydrochloride, menthol, or phenol)** with or without **topical corticosteroids**, such as triamcinolone oral paste 0.1% (Kenalog in Orabase®).
3. Agents containing hydrogen peroxide, iodine, and thyme derivatives may tend to worsen mouth ulcers. It is preferable to avoid these agents.
4. Antifungal agents must be avoided unless a fungal infection is diagnosed. In particular, systemic imidazole antifungal agents (ketoconazole, fluconazole, itraconazole, etc.) should be avoided in all patients due to their strong inhibition of everolimus metabolism, thereby leading to higher everolimus exposures. Therefore, topical

antifungal agents are preferred if an infection is diagnosed. Similarly, antiviral agents such as acyclovir should be avoided unless a viral infection is diagnosed.

Note: Stomatitis/oral mucositis should be appropriately graded using the functional grading given on the NCI-CTC for adverse events, CTCAE v 4.0. Dose reductions are made according to section 6.3.1 (Non-hematological toxicity) and Section 6.3.3.

6.2.2 Management of hyperlipidemia & hyperglycemia

Adverse Drug Reaction	Severity	Everolimus Dose Adjustment and Management Recommendations
Metabolic events (e.g. hyperglycemia, dyslipidemia)	Grade 1	No dose adjustment required. Initiate appropriate medical therapy and monitor.
	Grade 2	No dose adjustment required. Manage with appropriate medical therapy and monitor.
	Grade 3	Temporary dose interruption. Re-initiate everolimus at lower dose. Manage with appropriate medical therapy and monitor.
	Grade 4	Discontinue everolimus and treat with appropriate medical therapy.

Treatment of hyperlipidemia should take into account the pre-treatment status and dietary habits of the patient. Grade 2 or higher hypercholesterolemia (>300 mg/dL or 7.75 mmol/L) or grade 2 hypertriglyceridemia or higher (>2.5 x upper normal limit) should be treated with a 3-hydroxy-3-methyl-glutaryl (HMG)-CoA reductase inhibitor (e.g. atorvastatin, pravastatin, fluvastatin) or appropriate triglyceride-lowering medication, in addition to diet.

Note: Concomitant therapy with fibrates and an HMG-CoA reductase inhibitor is associated with an increased risk of a rare but serious skeletal muscle toxicity manifested by rhabdomyolysis, markedly elevated creatine phosphokinase (CPK) levels and myoglobinuria, acute renal failure and sometimes death. The risk versus benefit of using this therapy should be determined for individual patients based on their risk of cardiovascular complications of hyperlipidemia.

Dyslipidemia (including hypercholesterolemia and hypertriglyceridemia) has been reported in patients taking everolimus. Monitoring of blood cholesterol and triglycerides prior to the start of everolimus therapy and periodically thereafter as well as management with appropriate medical therapy is recommended.

Hyperglycemia has been reported in patients taking everolimus. Monitoring of fasting serum glucose is recommended prior to the start of everolimus and periodically thereafter. More frequent monitoring is recommended when everolimus is co-administered with other drugs that may induce hyperglycemia. Optimal glycemic control should be achieved before starting a patient on everolimus.

6.2.3 Management of non-infectious pneumonitis

Both asymptomatic radiological changes (grade 1) and symptomatic non-infectious pneumonitis (grade 2 = not interfering with activities of daily living or grade 3 = interfering with activities of daily living and oxygen indicated) have been noted in patients receiving everolimus therapy. Non-infectious pneumonitis has been associated with everolimus and other mTOR inhibitors (Atkins 2004). In order to monitor for asymptomatic (grade 1) pulmonary infiltrates, a chest X-ray is required if a CT scan of chest is not used for bi-monthly disease evaluations. Additional chest CT scans may be performed, when clinically necessary. If noninfectious pneumonitis develops, a consultation with a pulmonologist should be considered. If the patient develops grade 3 pneumonitis, treatment with everolimus should be interrupted and the patient should be treated as medically indicated (short course corticosteroids, oxygen, etc). Management of non-infectious pneumonitis suspected to be associated with everolimus and dose modifications instructions are provided in Table 6.2.3.

Table 6.2.3 Management of non-infectious pneumonitis

Worst grade pneumonitis	Suggested investigations	Management of pneumonitis	everolimus dose adjustment
Grade 1	CT scans with lung windows and pulmonary function testing including: spirometry, DLCO, and room air O ₂ saturation at rest. Repeat chest x-ray/CT scan every 2 Cycles until return to baseline.	No specific therapy is required	No dose adjustment required for Pazopanib or everolimus. Initiate appropriate monitoring.
Grade 2	CT scan with lung windows. Consider pulmonary function testing includes: spirometry, DLCO, and room air O ₂ saturation at rest. Consider a bronchoscopy with biopsy and/or BAL. Monitoring at each visit until return to ≤ grade 1 or baseline. Return to initial monitoring frequency if no recurrence.	Symptomatic only. Consider corticosteroids and/or other supportive therapy if symptoms are troublesome.	Rule out infection and consider interruption of everolimus (and optional pazopanib) until symptoms improve to Grade ≤ 1. Re-initiate everolimus at one dose level lower. Discontinue everolimus if failure to recover within ≤ 28 days. Pazopanib may resume at the discretion of the treating physician and principal investigator once toxicity is recovered to ≤ Grade 1 even if everolimus is discontinued.
Grade 3	CT scan with lung windows and pulmonary function testing includes: spirometry, DLCO, and room air O ₂ saturation at rest. Monitoring at each visit until return to ≤ grade 1. Return to initial monitoring frequency if no recurrence. Bronchoscopy with biopsy and/or BAL is recommended.	Consider corticosteroids if infective origin is ruled out. Taper as medically indicated.	Rule out infection and interrupt everolimus and pazopanib until symptoms improve to Grade ≤ 1. Consider re-initiating everolimus at one dose level lower (approximately 50% lower than the dose previously administered depending on individual clinical circumstances) Discontinue everolimus if failure to recover within ≤ 28 days. If toxicity recurs at Grade 3, consider discontinuation of everolimus. Pazopanib may resume at the discretion of the treating physician and principal investigator once toxicity is recovered to ≤ Grade 1 even if everolimus is discontinued.
Grade 4	CT scan with lung windows and required pulmonary function testing, if possible, includes: spirometry, DLCO, and room air O ₂ saturation at rest. Monitoring at each visit until return to ≤ grade 1. Return to initial monitoring frequency if no recurrence. Bronchoscopy with biopsy and/or BAL is recommended if possible.	Consider corticosteroids if infective origin is ruled out. Taper as medically indicated.	Rule out infection and discontinue everolimus. Pazopanib may resume at the discretion of the treating physician and principal investigator once toxicity is recovered to ≤ Grade 1 even if everolimus is discontinued.

* A bronchoscopy with biopsy and/or bronchoalveolar lavage is recommended.

6.2.4 Management of hepatitis reactivation / flare

Reactivation of Hepatitis B (HBV) has been observed in patients with cancer receiving chemotherapy (Yeo 2004). Sporadic cases of Hepatitis B reactivation have also been seen in this setting with everolimus. Use of antivirals during anti-cancer therapy has been shown to reduce the risk of Hepatitis B virus reactivation and associated morbidity and mortality (Loomba 2008). A detailed assessment of Hepatitis B/C medical history and risk factors must be done for all patients at screening, with testing performed prior to the first dose of everolimus.

Monitoring and prophylactic treatment for hepatitis B reactivation

Table 6.2.4.1 provides detail of monitoring and prophylactic therapy according to the screening results of viral load and serologic markers testing.

Table 6.2.4.1 Action to be taken based on screening hepatitis B results

Test	Result	Result	Result	Result	Result
HBV-DNA	+	+ or -	-	-	-
HBsAg	+ or -	+	-	-	-
HBsAb	+ or -	+ or -	+ and no prior HBV vaccination	+ or -	- or + with prior HBV vaccination
HBcAb	+ or -	+ or -	+ or -	+	-
Recommendation	Prophylaxis treatment should be started 1-2 weeks prior to first dose of everolimus Monitor HBV-DNA approximately every 4-8 weeks		No prophylaxis Monitor HBV-DNA approximately every 3-4 weeks		No specific action

Antiviral prophylaxis therapy should continue for at least 4 weeks after last dose of everolimus. For HBV reactivation definition and management guidelines, see Table 6.2.4.2

Table 6.2.4.2 Guidelines for the management of hepatitis B reactivation

HBV reactivation (with or without clinical signs and symptoms)*	
For patients with baseline results: Positive HBV-DNA OR positive HBsAg reactivation is defined as: [Increase of 1 log in HBV-DNA relative to baseline HBV-DNA value OR new appearance of measurable HBV-DNA]	Treat: Start a second antiviral medication AND Interrupt everolimus administration until resolution: 1. \leq baseline HBV-DNA levels If resolution occurs within ≤ 28 days, everolimus should be re-started at one dose lower, if available. If the patient is already receiving the lowest dose of everolimus according to the protocol, the patient should restart at the same dose after resolution. Both antiviral therapies should continue at least 4 weeks after last dose of everolimus. If resolution occurs > 28 days Patients should discontinue everolimus but continue both antiviral therapies at least 4 weeks after last dose of everolimus.
For patients with baseline results: Negative HBV-DNA and HBsAg AND [Positive HBsAb (with no prior history of vaccination against HBV), OR positive HBCAb] Reactivation is defined as: New appearance of measurable HBV-DNA	Treat : Start first antiviral medication AND Interrupt everolimus administration until resolution: 2. \leq undetectable (negative) HBV-DNA levels If resolution occurs within ≤ 28 days, everolimus should be re-started at one dose lower, if available. If the patient is already receiving the lowest dose of everolimus according to the protocol, the patient should restart at the same dose after resolution. Antiviral therapy should continue at least 4 weeks after last dose of everolimus. If resolution occurs > 28 days Patients should discontinue everolimus but continue antiviral therapy at least 4 weeks after last dose of everolimus.

* All reactivations of HBV are to be recorded as grade 3 (e.g. CTCAE Version 3.0 - Investigations/Other: Viral Reactivation), unless considered life threatening by the investigator, in which case they should be recorded as grade 4. Date of viral reactivation is the date on which the rise or reappearance of HBV-DNA was recorded.

Monitoring for hepatitis C flare

The following two categories of patients should be monitored every 4–8 weeks for HCV flare:

- Patients with detectable HCV RNA-PCR test at screening.
- Patients known to have a history of HCV infection, despite a negative viral load test at screening (including those that were treated and are considered ‘cured’)

For definitions of HCV flare and actions to be taken in the event of a flare, please refer to 6.2.4.3

Table 6.2.4.3 Guidelines for the management of hepatitis C flare

Baseline results	HCV flare definition*	HCV flare management
Detectable HCV-RNA	> 2 log ₁₀ IU/mL increase in HCV-RNA AND ALT elevation > 5 x ULN or 3 x baseline level, whichever is higher.	Discontinue everolimus
Knowledge of past hepatitis C infection with no detectable HCV-RNA	New appearance of detectable HCV-RNA AND ALT elevation > 5 x ULN or 3 x baseline level, whichever is higher.	Discontinue everolimus

* All flares of HCV are to be recorded as grade 3 (e.g. CTCAE Version 3.0 - Investigations - Other: Viral Flare), unless considered life threatening by the investigator; in which case they should be recorded as grade 4. Date of viral flare is the date on which both the clinical criteria described above were met. (e.g., for a patient whose HCV-RNA increased by 2 logs on 01 JAN 2011 and whose ALT reached > 5 x ULN on 22 JAN 2011, the date of viral flare is 22 JAN 2011).

6.2.5 Management of infections

Everolimus has immunosuppressive properties and may predispose patients to bacterial, fungal, viral or protozoal infections, including infections with opportunistic pathogens. Localized and systemic infections, including pneumonia, other bacterial infections, invasive fungal infections, such as aspergillosis or candidiasis and viral infections including reactivation of hepatitis B virus, have been described in patients taking everolimus. Some of these infections have been severe (e.g. leading to respiratory or hepatic failure) and occasionally have had a fatal outcome.

Physicians and patients should be aware of the increased risk of infection with everolimus. Treat pre-existing infections prior to starting treatment with everolimus. While taking everolimus, be vigilant for symptoms and signs of infection; if a diagnosis of infection is made, institute appropriate treatment promptly and consider interruption or discontinuation of everolimus.

If a diagnosis of invasive systemic fungal infection is made, discontinue everolimus and treat with appropriate antifungal therapy.

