Nine patients were enrolled in the phase I portion of this study. Two patients on dose level 0 (pazopanib 600 mg daily and everolimus 5 mg daily) experienced dose limiting toxicities (grade 3 rash and pruritus and grade 3 thrombocytopenia requiring a dose reduction). Therefore, three patients were treated at dose level -1 per protocol. None of these three patients experienced a protocol-defined dose-limiting toxicity. Therefore, another three patients were treated at dose level -1 (pazopanib 400 mg daily and everolimus 5 mg daily) without any dose-limiting toxicities. Therefore, per protocol, dose level -1 was defined as the maximum tolerated dose.

Toxicity	Maximum Grade			
	G1	G2	G3	G4
Febrile neutropenia	-	-	1	-
Neutropenia	1	-	-	-
Thrombocytopenia	3	1	1	-

Hematologic toxicities (see table above) included febrile neutropenia (11%), neutropenia (11%), thrombocytopenia (56%), and anemia (36%). Grade 3 febrile neutropenia and thrombocytopenia each occurred in 1 patient. Non-hematologic toxicities were varied, though many were expected based on the known toxicities of everolimus and pazopanib. One patient did experience a grade 3 pneumothorax, which was possibly related to study therapy. Other non-hematologic toxicities included anorexia (11%), bone pain (11%), diarrhea (22%, 11% G3), fatigue (56%), dysgeusia (11%), headache (11%), hypertension (22%), mucositis (33%), musculoskeletal (muscle stiffness after prolonged periods of sitting, 11%), nausea (44%), palmo-plantar erythrodysesthesia syndrome (11%), pneumonia (11% G3), pruritus (11% G3), rash (33%, 11% G3), vomiting (33%), and weight loss (11%). Toxicities noted in laboratory evaluations were generally consistent with what is expected with both agents administered separately. G3 and 4 laboratory toxicities included increased ALT, hypophosphatemia, and hypouricemia each in 1 patient, and increased lipase in 2 patients.

Treatment was generally well tolerated at the MTD. Two of 6 patients came off treatment after 2 cycles because of toxicity. The others stopped treatment due to disease progression or physician decision.

Antitumor activity

Encouraging antitumor activity was noted in the bladder cancer patients treated on pazopanib and everolimus. Of five urothelial cancer patients evaluable, 3 had stable disease for 4 months, 4 months and 5.5 months respectively. One patient had a complete response which lasted 14 months.

Tumor type	(n)	Best objective response

Bladder	5	3 SD, 1CR, 1 NE

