Pneumonitis is a recognized adverse effect of rapamycins (sirolimus, temsirolimus, and everolimus). Numerous case reports in the literature suggest that rapamycin-associated pneumonitis is relatively unaggressive, limited in extent, and reversible upon drug discontinuation. The term 'pneumonitis' is used here to describe non-infectious, nonmalignant infiltration in the lungs which is evident radiologically. More precise diagnosis should follow histocytological examination following lung biopsy, generally during bronchoscopy which may or may not be symptomatic. Advice on the management of pneumonitis has been provided in Table 6.2.3. In oncology studies with everolimus, severe pneumonitis suspected as drug-related has been reported as a serious adverse event on 13 occasions and additionally in the following associated preferred terms including acute respiratory distress syndrome (n=2), alveolitis (n=1) and allergic alveolitis (n=1), interstitial lung disease (n=10), lung infiltration (n=23), cryptogenic organizing pneumonia, lung consolidation, pulmonary alveolar haemorrhage, pulmonary toxicity and pulmonary fibrosis (n=1, each). One fatal case of drug-related pneumonitis was reported for a patient with metastatic infiltrating ductal carcinoma of the breast treated with 10 mg/day, which developed approximately two months after starting everolimus. Cytology for both the pleural and pericardial fluids were positive for malignancy. The death was considered possibly related to the underlying late stage tumor and study drug. Additionally, one patient treated

with 10 mg/day died due to severe acute respiratory distress syndrome and septic shock. Thoracic CT scan demonstrated condensation in the majority of the left lower lobe and frosted glass appearance in the left upper lobe, lingula, and right lung. Along with the cases of non-infectious pneumonitis, serious opportunistic infections have also been reported in cancer patients treated with everolimus: mycobactrium, aspergillus, and fatal candidal sepsis, and fatal pneumocystis carni in particular. Because everolimus, as other rapamycins, inhibits proliferation of activated lymphocytes and reduces neutrophil counts, treatment with everolimus must be considered as predisposing patients to the risk of infection. This risk will be higher in patients severely immunocompromised because of their underlying disease and/or co-medications. Outcome may be fatal in case of serious infections.

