6.2.6 Management of skin toxicity

For patients with grade 1 toxicity, no specific supportive care is usually needed or indicated. Rash must be reported as an AE. Patients with grade 2 or higher toxicity may be treated with the following suggested supportive measures at the discretion of the investigator: oral minocycline, topical tetracycline, topical clindamycin, topical silver sulfadiazine, diphenhydramine, oral prednisolone (short course), topical corticosteroids, or pimecrolimus.

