6.3 Dose Modifications/Delays

6.3.1 General dose modification/Delays

Dose modifications for toxicities not otherwise covered in section 6.2 are listed in the table below. Patients who do not recover to grade 2 or less toxicity within 28 days will be removed from protocol therapy except where noted (ie. pneumonitis). In addition, patients may hold study intervention (pazopanib and everolimus) for greater than 28 days if the patient's physician and the overall principal investigator, [name], agree that the patient is deriving clinical benefit from the study drugs. Dose modifications for specific toxicities are covered in sections 6.2 and 6.3.

All toxicities, both during the DLT period and after it has been completed, will follow the guidelines laid out here in sections 6.2 and 6.3.

For definition of a Dose Limiting Toxicity, refer back to section 5.4.

Non-hematological toxicity

Toxicity	Actions
Non-Infectious Pneumonitis	Please refer to section 6.2.3
Reactivation of HBV or HCV flare	Please refer to section 6.2.4
Non-hematological toxicity Grade 2 (except pneumonitis – refer to section 6.2.3) (except hypertension, proteinuria, venous or arterial thrombosis, QTc prolongation- refer to section 6.3.2) (except hepatotoxicity – refer to section 6.3.3) (except elevated amylase and lipase- refer to section 6.3.5)	If the toxicity is tolerable to the patient, maintain the same dose. If the toxicity is “intolerable” to patient, interrupt pazopanib and everolimus until recovery to grade ≤ 1 . Then reintroduce pazopanib and everolimus at same dose. If event returns to “intolerable” grade 2, then interrupt pazopanib and everolimus until recovery to grade ≤ 1 . Then reintroduce pazopanib and everolimus at one dose level lower. If event is recurrent “intolerable” grade 2 despite two dose reductions, discontinue pazopanib and everolimus.
Grade 3 or 4 (except hyperlipidemia ¹) (except pneumonitis – refer to section 6.2.3) (except hypertension, proteinuria, venous or arterial thrombosis, QTc prolongation- refer to section 6.3.2) (except hepatotoxicity – refer to section 6.3.3)	Interrupt pazopanib and everolimus until recovery to grade ≤ 1 . Then reintroduce pazopanib and everolimus at one dose level lower. No more than 2 dose reductions allowed.
Stomatitis / oral mucositis / mouth ulcers	See section 6.2.3 Management of stomatitis / oral mucositis / mouth ulcers

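### Sections 6.2.5 and 6.3.1 give differing dose instructions for a grade 3-4 infection, and the text does not settle which one governs

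*Combined protocol and SAP*

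**What the plan says.** **Infection (6.2.5).** The general instruction has no grade and names one drug: "if a diagnosis of infection is made, institute appropriate treatment promptly and consider interruption or discontinuation of everolimus". One subtype has a firm rule: "If a diagnosis of invasive systemic fungal infection is made, discontinue everolimus and treat with appropriate antifungal therapy". Pazopanib is not mentioned.

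**Skin toxicity (6.2.6).** For grade 2 and above the section offers optional supportive care and no dose instruction: "Patients with grade 2 or higher toxicity may be treated with the following suggested supportive measures at the discretion of the investigator".

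**Scope of the dose table (6.3.1).** The section opens with "Dose modifications for toxicities not otherwise covered in section 6.2 are listed in the table below". Shortly afterwards it says that all toxicities, during and after the DLT period, "will follow the guidelines laid out here in sections 6.2 and 6.3". The opening of 6.2 says the same.

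**Rows of the non-hematological table (6.3.1).** The general grade 3 or 4 row has both drugs interrupted until grade 1 or better, and continues: "Then reintroduce pazopanib and everolimus at one dose level lower. No more than 2 dose reductions allowed". Its exceptions are hyperlipidemia, pneumonitis, the vascular, renal and QTc events of 6.3.2, and hepatotoxicity. Neither infection nor rash is excepted. Further down, a row for grade 3 adverse events (and intolerable grade 2 mucositis) acts on everolimus only and restarts it at the unchanged dose if the event resolves within 7 days. A row for any other grade 4 event also acts on everolimus only, restarting one level lower if one is available.

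**Experience so far.** The Phase I update in 2.3 lists "pneumonia (11% G3), pruritus (11% G3), rash (33%, 11% G3" among the non-hematological toxicities of nine patients. Section 6.1.1 warns of infection on everolimus: "Outcome may be fatal in case of serious infections".

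**The concern.** An investigator facing a serious infection needs to know three things: whether everolimus must be held or only may be, whether pazopanib is held too, and at what dose treatment resumes. The protocol can be read to answer each of these differently depending on which passage is opened.

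This matters first for safety, since the protocol itself describes infections on everolimus as occasionally fatal. It also matters for exposure and withdrawals. In the expansion cohort, Table 6 in section 6 allows a single dose reduction. A patient reduced under the general grade 3 or 4 row has used it, and needing another ends study therapy unless the monotherapy provision applies. A patient managed under 6.2.5 may have used none. Eligibility criterion 3.3.1 and section 12.2 show two centers taking part in the expansion, so the same event could be handled in two ways within one small cohort.

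**Working it through.** No design figure of the plan is in question, so the check is a comparison of texts, followed by a rough sense of frequency.

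**Step 1. Instructions that can be read to apply to a grade 3-4 infection (invasive fungal infection aside).**

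| Place | Grade | Everolimus | Pazopanib |
|---|---|---|---|
| 6.2.5 | none stated | consider holding or stopping | silent |
| 6.3.1, general grade 3 or 4 row | 3-4 | hold, restart one level lower | hold, restart one level lower |
| 6.3.1, grade 3 adverse event row | 3 | hold; same dose if resolved within 7 days, otherwise one level lower if available | silent |
| 6.3.1, any other grade 4 row | 4 | hold, restart one level lower if available | silent |

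Take a grade 3 pneumonia in the expansion cohort that resolves in 5 days. Under 6.2.5 nothing is required beyond treating the infection and considering everolimus. Under the general row both drugs drop to the reduced level of Table 6. Under the grade 3 row everolimus returns at the same dose and pazopanib is not addressed. These are three different outcomes for one event.

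**Step 2. Does the scope text choose between them?** Two readings are possible.

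- *Reading A: having a section in 6.2 takes a toxicity out of the 6.3.1 table.* Infection is then governed by 6.2.5 alone. The conflict disappears, but pazopanib has no instruction. Grade 3-4 skin toxicity also leaves the table and, because 6.2.6 holds supportive care only, has no dose rule.
- *Reading B: the table applies unless a row excepts the toxicity or 6.2 supplies a dose rule that displaces it.* Rash is then dosed by 6.3.1. Infection meets 6.2.5 and the table rows together, unless an instruction to consider is itself taken to displace the table, which nothing states.

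The opening sentence of 6.3.1 favors A. The sentence sending all toxicities to both sections favors B. So does 6.2.1, where stomatitis has its own section yet is referred to 6.3.1 for dose reductions. The 6.3.1 table or its footnote names the topics of 6.2.1 to 6.2.4 (stomatitis, metabolic events, pneumonitis, hepatitis) but not those of 6.2.5 and 6.2.6, which looks like a drafting gap. Each reading leaves something unresolved.

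**Step 3. How often might it arise?** The input is grade 3 pneumonia in 1 of 9 Phase I patients (2.3): 1/9 = 11.1%, exact (Clopper-Pearson) 95% interval 0.3% to 48.2%. The expansion size is 29 in 14.1 and 25 in 1.1 and 14.2, so both are shown. The expected count is n × p, and the chance of at least one event is 1 − (1 − p)^n.

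| Assumed p | n = 29 | n = 25 |
|---|---|---|
| 11.1% | 3.2 events; 1 − (8/9)^29 = 0.97 | 2.8 events; 1 − (8/9)^25 = 0.95 |
| 5% (assumption) | 1.45 events; 1 − 0.95^29 = 0.77 | 1.25 events; 1 − 0.95^25 = 0.72 |
| 0.3% (lower limit) | 0.09 events; 1 − 0.997^29 = 0.08 | 0.08 events; 1 − 0.997^25 = 0.07 |

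At the upper limit at least one event is practically certain. The Phase I data therefore make such events plausible and say little about their rate.

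**The case against.** The best defense is that the opening sentence of 6.3.1 is itself a precedence rule: 6.2 comes first and the table takes the rest. Infection is then governed by 6.2.5 and nothing conflicts. In addition, 6.2.5 is ungraded and so must also serve mild infections, where discretion is natural. A site that holds and reduces both drugs for a grade 3 infection breaches neither 6.2.5 nor the general row. This has force: there is no flat contradiction between 6.2.5 and that row, only a difference between what one permits and the other requires. But the precedence reading is undercut by the second scope sentence and by the handling of stomatitis. It also does nothing about the grade 3 and grade 4 rows that differ from the general row inside the same table.

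A reader might infer that infection has two competing rules *and* that severe rash has none. The documents do not support both at once, because the two need opposite readings of one sentence. The no-rule reading for rash is the weaker: 6.2.6 contains no dose modification that could displace the table, rash is not excepted from it, and stomatitis shows that a 6.2 section can coexist with 6.3.1 dosing.

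A reader might also infer that 6.2.5 is discretionary throughout, or that 6.3.1 uniformly requires both drugs to be reduced. The fungal-infection directive answers the first and the everolimus-only rows answer the second.

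Finally, a reader might carry the 11% grade 3 rash figure into the expansion cohort, or suppose that these events would fall before the first 8-week scan. The one grade 3 rash is listed among the dose-limiting toxicities at dose level 0. At the expansion dose the count is therefore 0 of 6 (exact 95% interval 0% to 46%). For the pneumonia, 2.3 gives neither dose level nor timing. The monotherapy provision below Table 6 also means that a second reduction need not end all treatment for a patient with stable disease or better at restaging.

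**Conclusion.** The point holds as an inconsistency of instruction and scope. For a grade 3-4 infection, 6.2.5 and three rows of the 6.3.1 table differ on whether everolimus must be held, whether its dose is reduced, and whether pazopanib is affected. The two scope sentences of 6.3.1 do not settle which governs. For grade 3-4 skin toxicity, a dose rule exists under one reading of the scope sentence and not under the other; the reading that provides one is better supported, but it should not have to be inferred.

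The size cannot be stated with confidence. Serious infection in the expansion cohort is plausible on 1 of 9 patients with grade 3 pneumonia, assuming that nine patients at two dose levels are informative for it. No rate is claimed for rash at the expansion dose, and no effect on the timing of withdrawals is claimed. The point should be corrected because it bears on patient safety and costs little. It does not touch the sample size or the primary test.

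**What to change.** Reconcile 6.2.5, 6.2.6 and 6.3.1 in one amendment:

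1. Make the two scope sentences of 6.3.1 agree on whether a toxicity with its own 6.2 section is dosed by that section, by the table, or by both in a stated order.
2. Either name infection (6.2.5) and skin toxicity (6.2.6) in the exception lists of the table and put the dose rule in those sections, or state in those sections that the table governs dosing.
3. Resolve the overlap between the general grade 3 or 4 row, the grade 3 adverse event row and the any other grade 4 row. Without this, pointing to the table would still leave more than one instruction.
4. For each event, say whether the instruction covers pazopanib, and keep its relation to the fungal-infection directive explicit.

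The result should be one stated instruction for grade 3-4 infection and one for grade 3-4 skin toxicity. Which rule each contains is the sponsor's clinical decision. The cost is wording only, with no added procedures, visits or patients.
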